4.3.1 Concomitant treatment

Information about any treatment within 4 weeks prior to starting of DZD9008 and all concomitant treatments given during the study along with reasons for the treatment will be recorded in the Case Report Form (CRF). After permanent discontinuation of DZD9008 and 28 day follow up, only subsequent regimens of anti-cancer therapy will be recorded in CRF. If medically feasible, patients taking regular medication, with the exception of potent inhibitors and inducers of CYP3A4 (see Section 4.2 and Appendix H), should be maintained on it throught the study period.

All patients must avoid concomitant use of medications, herbal supplements and/or ingestions of food with known potent inducer/inhibitory effects on CYP3A activity whenever feasible. Traditional Chinese Medicine should be avoided. Such drugs must have been discontinued for 1 week (CYP3A4 inhibitors) or 2 weeks (CYP3A4 inducers) prior to first administration of DZD9008. Guidance on medications to avoid, medications that require close monitoring and on washout periods is given in Appendix H.

Patients must avoid live vaccines whist receiving study drug and up to 30 days after the last dose of study drug.

Patients may receive any medication that is clinically indicated for treatment of adverse events. All concomitant medications should be captured on the electronic CRF (eCRF).

Other anticancer agents, investigational agents and radiotherapy should not be given while the patient is receiving DZD9008. The patient may be allowed to take localized palliative radiotherapy only if it has been confirmed local lesion is not progressing, and/or after overall response has been evaluated as disease progression. This is to avoid interfering tumor assessment in the event of disease progression. Study drug interruption is not required in the case of local palliative radiotherapy for pain control (excluding chest and brain). For local

Date: July 24,2023

palliative radiotherapy to chest and brain, study drug should be interrupted during and up to 7 days post the palliative radiotherapy. Definitive radiotherapy and other anticancer therapy is not allowed.

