7.5 Calculation or derivation of tumor response variables

Independent Central Review of RECIST based assessments

The Independent Review Committee (IRC) will review all the images collected from Part B of the study and images collected from patients with EGFR Exon20ins in Part A of the study when needed. IRC review of all radiological imaging data will be carried out using RECIST version 1.1. All radiological scans for all patients (including those at unscheduled visits, or outside visit windows) will be provided to the IRC. Prior radiotherapy reports for patients (at baseline) and information on biopsied lesions will also be provided to the IRC to allow the selection of appropriate target lesions. The imaging scans will be reviewed by two independent radiologists using RECIST 1.1 criteria and will be adjudicated if required. For each patient, the IRC will define the overall visit response data (CR, PR, SD, PD or NE) and the relevant scan dates for each time point (i.e. for visits where response or progression is/is not identified). If a patient has had a tumor assessment which cannot be evaluated then the patient will be assigned a visit response of not evaluable (NE) (unless there is evidence of progression in which case the response will be assigned as PD). Endpoints (ORR, DoR, DCR, PFS) will be derived from the scan dates. ORR will only include patients whose response has been confirmed by a second scan at least 4 weeks after the initial response. The endpoint of tumor shrinkage will be assessed from tumor size measurements based on the primary independent radiologist assessment.

Date: July 24,2023

Results from the independent review will not be communicated to investigators. The management of patients will be based solely on the results of the RECIST 1.1 assessment conducted by the investigator.

For more detailed information refers to recent IRC charter.

Investigator RECIST based assessments

From the investigators review of the imaging scans, the RECIST tumor response data will be used to determine each subject's visit response according to RECIST version 1.1. At each visit, patients will be assigned a RECIST 1.1 visit response of CR, PR, SD or PD depending on the status of their disease compared with baseline and previous assessments.

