This appendix details the implementation of RECIST (Response Evaluation Criteria in Solid Tumors) 1.1 guidelines (Eisenhauer et al 2009) for the study with regards to investigator assessment of tumor burden including protocol-specific requirements for this study.

Definition of measurable, non-measurable, target and non-target lesions

Patients with at least one lesion measurable that can be accurately assessed at baseline by computerized tomography (CT), magnetic resonance imaging (MRI) or plain X-ray should be included in this study.

Measurable lesions

At least one lesion, not previously irradiated, that can be accurately measured at baseline as \geq 10 mm in the longest diameter (except lymph nodes which must have short access \geq 15mm) with computered tomography (CT) or magnetic resonance imaging (MRI) which is suitable for accurate repeated measurements.

Non-measurable lesions

- All other lesions, including small lesions (longest diameter < 10 mm or pathological lymph nodes with ≥ 10 mm to < 15 mm short axis at baseline. Nodes with < 10 mm short axis are considered non-pathological and should not be recorded as non-target lesions (NTLs)
- Truly non-measurable lesions include the following: bone lesions, leptomeningeal disease, ascites, pleural / pericardial effusion, inflammatory breast disease, lymphangitic involvement of skin or lung, abdominal masses/abdominal organomegaly identified by physical examination that are not measurable by CT or MRI
- Previously irradiated lesions as localized post-radiation changes, which affect lesion sizes, may occur. Therefore, lesions that have been previously irradiated will not be considered measurable and should be selected as NTLs at baseline and followed up as part of the NTL assessment
- Skin lesions assessed by clinical examination
- Brain metastasis

Special cases

• Lytic bone lesions or mixed lytic-blastic lesions, with identifiable soft tissue components, can be considered measurable if the soft tissue component meets the definition of measurability. Blastic lesions are considered non-measurable.

Date: July 24,2023

Cystic metastases can be considered measurable lesions if they meet the criteria for
measurability from a radiological point of view, but if non-cystic lesions are present in
the same patient, these non-cystic lesions should be selected as the target lesions (TLs).

Target lesions

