A maximum of 5 measurable lesions, with a maximum of 2 lesions per organ (including lymph nodes), representative of all lesions involved, should be identified as TLs at baseline. Target lesions should be selected on the basis of their size (longest diameter for non-nodal lesions or short axis for nodal lesions) but in addition should be those that lend themselves to reproducible

Date: July 24,2023

repeated measurements. It may be the case that, on occasion, the largest lesion does not lend itself to reproducible measurement in which circumstance the next largest lesion, which can be measured reproducibly, should be selected.

The site and location of each TL should be documented as well as the longest diameter for non-nodal lesions (or short axis for lymph nodes). All measurements should be recorded in millimeters. At baseline, the sum of the diameters for all TLs will be calculated and reported as the baseline sum of diameters. At follow-up visits the sum of diameters for all TLs will be calculated and reported as the follow-up sum of diameters.

Special cases:

- For TLs measurable in 2 or 3 dimensions, always report the longest diameter. For pathological lymph nodes measurable in 2 or 3 dimensions, always report the short axis.
- If the CT/MRI slice thickness used is > 5mm, the minimum size of measurable disease at baseline should be twice the slice thickness of the baseline scan.
- If a lesion has completely disappeared, the longest diameter should be recorded as 0 mm.
- If a TL splits into two or more parts, then record the sum of the diameters of those parts
- If two or more TLs merge then the sum of the diameters of the combined lesion should be recorded for one of the lesions and 0 mm recorded for the other lesion(s)
- If a TL is believed to be present and is faintly seen but too small to measure, a default value of 5 mm should be assigned. If an accurate measure can be given, this should be recorded, even if it is below 5mm.
- If a TL cannot be measured accurately due to it being too large, provide an estimate of the size of the lesion
- When a TL has had any intervention e.g., radiotherapy, embolization, surgery etc., during the study, the size of the TL should still be provided where possible

Evaluation of target lesions

Table 20 provides the definitions of the criteria used to determine objective tumor visit response for TLs.

Table 20 Overall Visit Response for Target Lesions

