Complete Response (CR)	Disappearance of all TLs since baseline. Any pathological lymph nodes selected as TLs must have a reduction in short axis to < 10 mm.
Partial Response (PR)	At least a 30% decrease in the sum of diameters of TLs, taking as reference the baseline sum of diameters.

Stable Disease (SD)

Neither sufficient shrinkage to qualify for PR nor sufficient increase to qualify for PD.

Progressive Disease (PD)

At least a 20% increase in the sum of diameters of TLs, taking as reference the smallest sum on study (this includes the baseline sum if that is the smallest on study). In addition to the relative increase of 20%, the sum must also demonstrate an absolute increase of at least 5mm.

Not Evaluable (NE)

Only relevant if any of the TLs were not assessed or not evaluable or had a lesion intervention at this visit.

Note: If the sum of diameters meets the progressive disease criteria,

Non-Target lesions

Evaluation of non-target lesions

All other lesions (or sites of disease) not recorded as TLs should be identified as NTLs at baseline. Measurements are not required for these lesions but their status should be followed at subsequent visits. At each visit, an overall assessment of the NTL response should be recorded by the investigator. Table 21 provides the definitions of the criteria used to determine and record overall response for NTLs at the investigational site at each visit.

progressive disease overrides not evaluable as a TL response

Table 21 Overall Visit Response for Non-Target Lesions

Complete Response (CR)	Disappearance of all NTLs since baseline. All lymph nodes must be non-pathological in size (< 10 mm short axis).
Non-CR/Non-PD	Persistence of one or more NTLs.
Progressive Disease (PD)	Unequivocal progression of existing NTLs. Unequivocal progression may be due to an important progression in one lesion only or in several lesions. In all cases the progression MUST clinically significant for the physician to consider changing or stopping therapy.
Not Evaluable (NE)	Only relevant when one or some of the NTLs were not assessed and in the investigator's opinion they are not able to provide an evaluable overall NTL assessment at this visit.
	Note: For patients without TLs at baseline, this is relevant if any of the NTLs were not assessed at this visit and the progression criteria have not been met.

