2.1.1 Primary Objective and Estimand

Objectives	Endpoint/Estimand Description	
To evaluate anti-tumor activity of DZD9008 in advanced NSCLC patients with EGFR Exon20ins at defined dose(s) by assessment of Objective Response Rate (ORR)	Endpoint: Objective Response Rate (ORR) according to Response Evaluation Criteria in Solid Tumors (RECIST) version 1.1 evaluated by an Independent Review Committee (IRC), where confirmation of response is required.	
	Estimand Description:	
	Treatment: DZD9008 200 mg or 300 mg QD.	
	Population: Full Analysis Set (FAS) will be used for analysis, including all the NSCLC patients with documented EGFR Exon20ins mutations in tumor tissue, who were previously treated with platinumbased chemotherapy, received at least one dose of DZD9008, have at least one measurable lesion at baseline as identified by IRC.	
	Variable: Binary variable indicating whether patient is a responder who achieved confirmed complete response (CR) or partial response (PR) prior to progressive disease (PD), as evaluated by IRC according to RECIST 1.1;	

Objectives	Endpoint/Estimand Description	
	Intercurrent Event with Strategy:	
	PD evaluated by IRC	
	While on treatment strategy: the intercurrent event is already captured in the variable definition	
	Treatment Discontinuation due to reason other than PD evaluated by IRC	
	Treatment policy strategy: Intercurrent event is ignored, tumor response data irrespective of treatment discontinuation are considered in analysis.	
	New Anticancer Therapy	
	While on treatment strategy: Only the tumor response data prior to start of the new anticancer therapy are of interest.	
	Population-level Summary: Confirmed ORR, which is defined as the proportion of responders.	

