4.2.1 Primary Efficacy Endpoint

The primary efficacy endpoint is ORR according to RECIST 1.1 assessed by IRC, where confirmation of response is required.

ORR is defined as the percentage of patients who have best overall response (BOR) of Complete Response (CR) or Partial Response (PR) prior to any evidence of progression (as evaluated by IRC based on RECIST 1.1). Any CR or PR which occur after a further anticancer therapy is received will not be included in numerator of the ORR calculation, where further anticancer therapy (also called as new anticancer therapy) includes the systematic anticancer therapy or definitive radiothrapy received for the study indication after first dose of DZD9008.

In part B of study, RECIST assessments will be performed by IRC and investigator independently, from Cycle 3 Day 1 (\pm 7 days) and then every 6 weeks (\pm 7 days). A visit overall response of CR is defined when all Target Lesion (TL) and Non-Target Lesion (NTL) lesions present at baseline have disappeared (with the exception of lymph nodes which must have short axis < 10 mm to be considered non-pathological) and no new lesions have developed since baseline. A visit response of PR is defined when the sum of diameters of the TLs has decreased by 30% or more compared to baseline (with no evidence of progression) and the NTLs are at least stable with no evidence of new lesions. More details regarding RECIST assessment can be found in the appendix F of CSP.

BOR is defined as the best response recorded from first dose of DZD9008 until RECIST progression is documented for each patient. BOR represents the best response that a patient has had prior to any subsequent cancer therapy received, irrespective of whether or not patients discontinued treatment of DZD9008. There are 5 potential categories for BOR (from best to worst): CR, PR, Stable Disease (SD), Progressive Disease (PD) and Not Evaluable (NE). When SD is believed to be the best response, at least 35 days from first dose (6 weeks minus 7-day visit window) is required.

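### Shrinkage of a target lesion after permitted palliative radiotherapy can count toward confirmed IRC ORR, because neither the responder rule nor the lesion rule clearly excludes it

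*SAP*

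**What the plan says.** **Therapy-level rule.** SAP 4.2.1 leaves out of the ORR numerator any response that occurs after further anticancer therapy, which "includes the systematic anticancer therapy or definitive radiothrapy received for the study indication after first dose of DZD9008". The estimand in SAP 2.1.1 has the same aim: "Only the tumor response data prior to start of the new anticancer therapy are of interest". Palliative radiotherapy is neither in that definition nor listed as an intercurrent event.

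**Permitted treatment.** Protocol 4.3.1 states: "The patient may be allowed to take localized palliative radiotherapy only if it has been confirmed local lesion is not progressing", and/or once the overall response has been called progression. Chest and brain are covered, with an interruption of study drug. For patients on drug, "Definitive radiotherapy and other anticancer therapy is not allowed".

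**Lesion-level rule.** SAP 4.2.1 refers to protocol Appendix F for RECIST detail. Table 20 there describes NE for target lesions (TLs) as follows: "Only relevant if any of the TLs were not assessed or not evaluable or had a lesion intervention at this visit", with progression overriding. Table 22 turns a target-lesion NE into an overall NE when there is no progression or new lesion. For a TL that had radiotherapy, embolization or surgery on study, "the size of the TL should still be provided where possible". At baseline the appendix is stricter: "lesions that have been previously irradiated will not be considered measurable and should be selected as NTLs at baseline", because post-radiation changes can affect lesion size. The appendix introduces itself as covering investigator assessment.

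**What the IRC receives.** Protocol 7.5 says: "Prior radiotherapy reports for patients (at baseline) and information on biopsied lesions will also be provided to the IRC", so that suitable target lesions can be chosen. Protocol 7.5 and SAP 4.2 leave further detail to the IRC charter. SAP 4.2.1 does not use the IRC's own best overall response, because the IRC derivation ignored new anticancer therapy.

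**The concern.** The therapy-level rule exists so that a response is credited to DZD9008 and not to something else. It names the radiotherapy that is barred on treatment and omits the radiotherapy that is allowed. The lesion-level rule should catch what the first rule misses, but its wording reaches one visit only and is not tied to the IRC read.

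Confirmed ORR by IRC is the only primary endpoint of Part B. It is tested in each arm against a fixed 17% (protocol 7.9.7.1), with no arm that does not receive DZD9008. A patient with stable disease whose irradiated chest lesion later shrinks enough at two visits would become a confirmed responder. Best overall response, time to response, membership of the duration-of-response set and best tumor change (SAP 4.2.2.4, same cut-off) would follow.

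**Working it through.** **1. Can the sequence occur under the written rules?** Scans fall at Cycle 3 Day 1 (week 6) and then every 6 weeks.

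| Week | Event | Visit response |
|---|---|---|
| 6 | First scan | SD |
| between 6 and 12 | Palliative radiotherapy to a TL that is not progressing | – |
| 12 | Table 20 applied | NE |
| 18 | Sum at least 30% below baseline | PR |
| 24 | Same | PR |

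Nothing in Table 20 says that weeks 18 and 24 stay NE. SAP Table 1 scores PR followed by PR as PR, and 6 weeks exceeds the 28 days needed for confirmation. The therapy-level cut-off is not triggered. The patient is a confirmed responder.

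**2. How much must the irradiated lesion shrink?** Let w be its share of the baseline sum and hold the other TLs constant. A 30% fall in the sum needs the lesion to shrink by 0.30/w.

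- w = 1 (single TL): 30%.
- w = 0.5: 60%.
- w = 0.3: 100%.
- Five equal TLs, w = 0.2: not reachable, since complete disappearance lowers the sum by only 20%.

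The route is open mainly to patients with one or two dominant TLs, or with some shrinkage elsewhere. The w values are illustrative.

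**3. The plan's decision rule.** Inputs:

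- stop if 7 or fewer of 39 respond (protocol 5.3.3);
- N = 103 per arm, one-sided level 0.0125 and expected ORR 0.30 (SAP 2.4);
- null ORR 0.17 (protocol 7.9.7.1);
- 80% power, which appears only in the amendment log for version 8.0 and is taken as an assumption.

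The final boundary r is blacked out in the SAP, so it was solved for:

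P(reject | p) = sum over x = 8 to 39 of P(Bin(39, p) = x) × P(Bin(64, p) ≥ r − x)

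| r of 103 | Error at ORR 0.17 | Power at ORR 0.30 |
|---|---|---|
| 28 | 0.0060 | 0.746 |
| 27 | 0.0111 | 0.801 |
| 26 | 0.0196 | 0.845 |
| 25 | 0.0326 | 0.878 |

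The smallest r with error at most 0.0125 is 27 (27/103 = 26.2%), with power 0.801. The planned N = 103 is consistent with this.

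**4. Sensitivity at the boundary.** Each extra responder adds 1/103 = 0.97 percentage points. One such responder in the total lowers the number of true responders needed to 26, and two lower it to 25, with the stage 1 rule unchanged. The errors are then 0.0196 and 0.0326.

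**5. The same question as a rate.** Suppose a share m of true non-responders is scored as confirmed responders. The observed rate is 0.17 + 0.83m, tested at 27/103. Expected extra responders are 103 × 0.83 × m.

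| m (assumed) | Observed rate | Expected extra responders | Error |
|---|---|---|---|
| 0.5% | 0.1741 | 0.43 | 0.0151 |
| 1% | 0.1783 | 0.85 | 0.0201 |
| 2% | 0.1866 | 1.71 | 0.0340 |

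The documents give no value for m, and m = 0 is possible.

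**The case against.** The strongest reply is that the primary endpoint is an IRC read governed by a charter we cannot see. The amendment log for version 3.0 records that a rule on missing target lesions was moved from section 7.5 into that charter, so target-lesion handling for the IRC may well be settled there. This stands, and it limits confidence. It does not reach the SAP's own definition of further anticancer therapy, which the SAP applies itself.

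Next, Table 20 does score a treated lesion NE, and its visit wording is ambiguous rather than an instruction to make the lesion evaluable again. Recording the size is needed anyway, because progression overrides NE. Both points are fair. The gap is that nothing carries NE forward.

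Third, exposure is narrow. Pre-progression radiotherapy is conditional on a lesion that is not progressing, responses after progression never count, and brain metastases and most bone lesions are not measurable. One lesion must also move the whole sum by 30% at two visits. This stands, and step 2 supports it.

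Some stronger readings are tempting but not supported:

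- **Resection uses the same route.** Appendix F names surgery as a possible intervention, but no passage lists tumor resection as permitted, and 4.3.1 bars other anticancer therapy.
- **The IRC is kept unaware of on-study radiotherapy.** Protocol 7.5 names baseline reports; it does not say that nothing else is sent.
- **Disease control rate is inflated.** A patient moved from SD to PR was already counted.
- **The error is always upward.** NE at what would be the confirming visit can turn a genuine PR into SD under SAP Table 1.

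**Conclusion.** The gap is real as a matter of text. Unless the charter closes it, shrinkage of an irradiated target lesion at later visits can count toward confirmed IRC ORR. This is a specific omission in the primary endpoint rule, and more than missing detail.

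Its size is unknown and probably small, because the documents give no frequency of on-study radiotherapy to target lesions. A reader might infer from the working that the trial's true type I error is 0.020 or 0.033. It does not show that. Those figures say what one or two such responders would mean if the result fell at the boundary, they rest on an inferred boundary of 27/103, and they are not estimates of the error rate. No sample-size figure in the plan is found wrong.

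**What to change.** - **SAP 4.2.1 and 4.2.2.4.** State, for both the IRC-based and investigator-based derivations, that local treatment of a target lesion after first dose makes the target-lesion response NE at that and all later visits unless progression criteria are met.
- **Appendix F Table 20.** Replace the visit wording with: *at or before this visit, after baseline*.
- **Protocol 7.5 and the IRC charter.** Supply dates and sites of on-study radiotherapy and procedures to the IRC, and align the charter with the rule above.
- **Reporting.** List every responder with local treatment of a target lesion. A PR first seen before the treatment but confirmed only after it would lose its confirmation under carried-forward NE. Removing such patients is debatable, so report a sensitivity ORR that handles them the other way.

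The cost is wording in the SAP, appendix and charter, plus a data transfer. Protocol 4.3.1 already requires concomitant treatments and their reasons in the CRF; whether the form captures the irradiated site should be checked. ORR may fall slightly if a true responder had a target lesion irradiated. N, the significance level and the boundary stay as they are, and no change is proposed to who may receive radiotherapy.
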